Group 2 (or experimental EmoLED protocol group) will be visited once a week. Therapy in this case includes, in addition to the standard therapy, a treatment with EmoLED device; it consists in irradiating each 5 cm diameter area of the lesion for 60 seconds, with the blue light emitted by the device. For lesions larger than 5 cm, several applications will be applied on adjacent areas, until the whole lesion is covered.

EmoLED is a medical device for light therapy (Class IIa), portable and battery-powered. Its intended use is the care of acute and chronic skin lesions by healthcare staff on patients over 16 years old, regardless of their ethnicity. Related adverse events, incidents or side effects haven't been observed during previous clinical trials and clinical experiences; therefore, no risks are reported in addition to the ones related to the use of light in medicine. However, the device is labelled and written instructions are provided for a safe use.

The objective of the study is to assess eventual differences in the outcome between the two groups and to determine if the therapy of Group 2 is a valid alternative to the standard therapy in terms of healing rate, quality of life and economic impact:

- The primary endpoint of the study is the percentage/rate of lesion area reduction
- The secondary endpoints are, together with other clinical parameters aimed at evaluating the general clinical situation, quality of life and costs related to the two treatments.

There is a follow-up after 4 weeks since the end of the period of observation (it may end at the 16th week or earlier).

Ethical considerations

The study will be submitted to the Ethical Committee of each investigator hospital for approval and in any case will be performed according to the GCP, the Helsinki Declaration and the Italian laws and requirements in the matter of human clinical trials.

L.U.C.E. Study Protocol version 3.0 (24/02/2020)

10

Informed consent procedure

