As further detailed in the section on statistical analysis, it is expected to register, during the time of observation, a difference in efficacy between EmoLED protocol group ("Group 2") and SOC protocol group ("Group 1"), in terms of "healing rate", intended as a reduction of the wound area, but also as a progress, in a broad sense, of the overall clinical situation of the lesion, in terms of pain and quality of life.

Endpoint

Primary endpoint of the study

The primary endpoint will be the outcomes comparison in terms of healing rate of lesions treated with SOC only versus lesions treated with EmoLED and SOC, on week 16th.

L.U.C.E. Study Protocol version 3.0 (24/02/2020)

Secondary endpoint

- 1) Safety of treatment
- 2) Evaluation of the healing time of the lesions treated with the standard method (Group 1) versus the lesions treated with the EmoLED Protocol (group 2);
- Evaluation of the treatment of chronic ulcers in patients undergoing standard treatment versus EmoLED treatment about life quality (QoL) in 16 weeks, through generic questionnaires as the EuroQiL-5D2 and specific questionnaires as the Wound-Qol3;
- 4) Evaluation of costs related to the treatment and control group, in both the NHS and society perspective
- 5) Evaluation of VAS scale in both groups;
- 6) Evaluation of satisfaction, complexity and helpfulness of EmoLED device, considering both the perspective of patients, and the one of doctors and health care workers involved;
- 7) Evaluation of cost-effectiveness using EmoLED for the treatment of ulcers.

Measurable parameters

The key data and lesion's pictures of each patient will be collected in the Data Collection Form, after the enrollment and the signature of the Informed Consent:

- Group 1: V1 (Visit 1 and first treatment), V2, V3, V4... until V32 (32 treatments are planned during 16 weeks, 2 per week)
- Group 2: V1 (Visit 1 and first treatment), V2, V3, V4... until V16 (16 treatments are planned during 16 weeks, 1 per week)

The parameters used to define the study result will be found through:

- Photographic images of lesions treated with EmoLED and control lesions
- Data Collection Form filled by the medical staff during the visit
- Economic/organizational impact survey
- Medical/clinical/social impact survey
- Survey on the usability of the device
- Detection of pain through VAS scale

Registration of clinical data

The data related to the evaluation of the study endpoints are acquired, for both groups, during the visits.

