The parameters of the Data Collection Form are acquired and kept on paper for the clinical trial lenght, and conserved in both paper and digital form; the pictures of the lesion are acquired and kept in digital form, during the length of the clinical trial and afterwards.

During each visit, a picture of the lesion will be taken so that the process of healing can be valued also in a visual way. Each picture will be named with the patient code and the date of the visit. In case of multiple lesions matching with both inclusion and exclusion criteria, they will be all treated following the same protocol, depending on the group of treatment, but only the lesion with the wider area will be registered; to distinguish the area of interest, the perilesional tissue will be labelled with single-use permanent markers.

Data Collection Form

The Data Collection Form is unique for each patient and includes: Clinical Section, Quality Life Section and Economic Section. The Clinical Section contains identification code of the patient, date of birth, sex, etiology of the ulcer, any eventual concurrent disease, any drug therapy (in terms of active substances), ulcer's date of onset, date of entry to the facility.

The second part of the form is organized as a matrix where the row represents the measurable parameters for each time of observation (reported in column).

The investigator marks with an "X" the chosen value for each parameter and the most suitable description. The Principal Investigator will also fill a check list, for each visit, to ensure that also the pain level has been measured and that the picture of the lesion has been taken.

There is also a "Notes" section to register information not planned at first, that might be helpful during the data analysis.

The last part of the Data Collection Form is about follow-up visit (after 4 weeks).

The Data Collection Form is already completed with the patient's recruitment code and the group they belong to, so that the allocation to the EmoLED group and the control group is random. The allocation sequence of the group is generated by Matlab.

On each visit, the patient will be asked to rate their current pain level (VAS scale 0-10).

The quality section survey will be administered on the first and last visits, and also every 4 weeks. In detail, standard questionnaires as the EQ-5D2 and the Wound-Qol3 will be administered, both available and validated in Italian language.

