Specific questionnaires for recognition of costs (Economic section) will be administered to patients and their primary caregiver (if present) during the first visit, with the aim of identifying the resources absorbed by the patients (and their caregivers) treated in the two different approaches. The consumption of resources will be measured by gathering information about the quantification of direct health costs (visits, hospitalizations, emergency healthcare, medications etc...), direct non-health-related costs (informal medical assistance, transportation and accommodation costs for each visit etc...) and indirect costs (productivity loss for both the patient and the caregiver/s) and also by taking into account both the costs associated with the adherence to the treatment, taking the first visit as a reference parameter, and the costs related to complications and events associated with the ulcer that determined the need for treatments/ exams and/or medical evaluations. The Principal Investigator will be given also a questionnaire to determine the costs incurred by their facility for handling patients with leg ulcers.

The questionnaires meant to value customer satisfaction, complexity and helpfulness of EmoLED device will be administered to doctors and to healthcare personnel involved in the treatment at the end of the trial.

Image Acquisition

For the 16 weeks of the trial, during each visit a picture of the lesion will be taken, so that the process of healing can be valued also in a visual way. Each picture will be named with the patient code and the date of the visit. The quantitative analysis about the size of the lesions through the collected pictures will be performed at certain time points: at the beginning, in the middle and at the end of the treatment.

The image analysis is made through an appropriate analysis algorithm that measures the area of the lesion (mm²). The lesion must be fully and frontally framed to obtain an optimal analysis. The ruler with patient's ID code and date must appear in every picture. It is important that the ruler is placed straight and in-focus to have the scale reference. If there is a wide lesion that needs more than one picture it's advisable to

L.U.C.E. Study Protocol version 3.0 (24/02/2020)

locate several markers around the lesion and take photos of adjacent areas, including at least two visible markers of the previous picture, to have the complete image of the lesion through a sequential photo array.

Bias

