The staff participating in the study is trained on the correct use of the device and accessories, as well as on the correct execution of the clinical protocol and on the compilation of the related forms. In any case, the EMOLED staff is always available to the team for any clarification or doubt during the study. In order to promote a more homogeneous operation between the various centres, joint training sessions are organized and documents which serve as guidelines for the most critical passages or the ones which require particular attention, such as recording, saving and transmitting data, are prepared. In order to avoid bias during the procedure of allocation in groups of patients enrolled in the study, it should be noted that the randomization grid is not distributed to the investigators: instead, paper folders are distributed containing the data collection forms. The progressive patient ID is on the outside of the folders, while on the inside a label is placed with the assignment of the patient to one of the two groups (Control or EmoLED treatment), which reflects the randomization grid. These folders are closed through an adhesive label with the signature of the Head of Clinical Affairs of the sponsoring company.

Patients selection

All patients that satisfy all the inclusion criteria, both hospitalised and outpatient, will be considered for inclusion in this study.

It will be used a standard procedure to value patients that includes the anamnesis evaluation and a physical examination.

Inclusion criteria

- Subjects suffering from venous and mixed skin ulcers;
- Presence of a lesion < 100 cm² of area and < 1 cm in depth;
- Men and women ≥ 18 years old;
- The patient must be able to understand the aims of the clinical trial and provide informed consent in writing;
- Chronicity of the lesion: at least 8 weeks.

Exclusion criteria

- Patients who participated in clinical trials about skin ulcers healing during the previous month;
- Patients who are not able to understand the aims of the trial;
- Patients with pressure ulcers;
- Patients with diabetic foot ulcers;
- Patients with circumferential leg ulcer (due to the difficulties in analysing the pictures);
- Patients with clearly infected ulcers or with systemic infection;
- Patients with ulcers caused by critical ischemia;
- Patients with a self-harm past that can purposely alter the process of healing;
- Patients with psychiatric disorders;

L.U.C.E. Study Protocol version 3.0 (24/02/2020)

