80 patients will be recruited during the study; they will be randomized 1:1 to the standard treatment group and the EmoLED Protocol group. In the control group, which follows the standard treatment, patients will be visited twice a week. The EmoLED experimental Protocol group will undergo medical examination once a week; in this case, therapy will consist in the standard treatment plus EmoLED treatment.

This sample size is sufficient to compare the average rate of the injured area reduction, considering Student-T test for the comparison between independent samples, by establishing $\alpha = 0.05$, power level (1- β) = 0,8, under the assumption to have an area reduction rate after 16 weeks amounting to 50% in Group 1 (control group), a difference of 20% between Group 2 (experimental group) and Group 1, a standard deviation of averages equal to 50% of the mean values and a bilateral hypothesis.

Statistical analysis

The average rate of reduction of the injured area between the two groups will be compared using the Student-T-test, the quality of life in both groups at the baseline, after 16 weeks and the difference with the baseline will be compared using Student-T-test for independent samples.

Linear regression models will be used to value the differences between the groups to exclude any confounding factors. Due to the usually asymmetrical nature of cost distribution, the comparison of the costs related to the treatment and control group, in both the NHS and society perspective, will be made using the non-parametric Mann-Whitney U test.

Generalized linear regression models will be used to value the differences between the groups to eliminate any confounding factors.

The cost-effectiveness of both treatments in the time frame of the study (16 weeks) will be valued by calculating the incremental cost-effectiveness ratio (ICER) and expressed in terms of incremental costs for "quality adjusted years (QALY).

Extrapolations of results about the cost-effectiveness that simulate longer time-frames will be made considering decision-making models (e.g. Markov models) and eventually including the data gathered during the study with literary data and/or evidence from other studies.

Data publication policy

L.U.C.E. Study Protocol version 3.0 (24/02/2020)

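### The primary week-16 comparison of percent area reduction does not adjust for baseline lesion area, which is already measured; naming it as a covariate would gain precision at almost no cost

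*Combined protocol and SAP*

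**What the plan says.** - **Entry.** Inclusion criteria: "Presence of a lesion < 100 cm² of area and < 1 cm in depth". No inclusion or exclusion criterion sets a minimum area.
- **Primary measure.** Objectives of the study: "The primary endpoint of the study is the percentage/rate of lesion area reduction". The endpoint section places the comparison at week 16.
- **Primary test.** Statistical analysis: "The average rate of reduction of the injured area between the two groups will be compared using the Student-T-test". No covariate is mentioned.
- **Regression.** The same section adds: "Linear regression models will be used to value the differences between the groups to exclude any confounding factors". It does not say which outcome or which covariates, or whether this model or the t-test decides the primary result.
- **Allocation.** Data Collection Form: "The allocation sequence of the group is generated by Matlab". The Bias section describes sealed folders. Neither mentions stratification by lesion size.
- **Baseline area.** Image Acquisition has lesion area measured from photographs "at the beginning, in the middle and at the end of the treatment", so a starting area is planned for every patient.

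**The concern.** Percent reduction is computed against the starting area. If lesions close from the edge, the same advance of the wound margin removes a larger share of a small lesion than of a large one. With entry open to anything under 100 cm², part of the spread in the endpoint may therefore reflect starting size alone. A t-test leaves that part in the error term, and if one arm happens to receive smaller lesions, the estimate is not corrected for it.

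The regression sentence could supply the correction but is too general to do so. If an adjusted model and the t-test disagree, the plan does not say which one counts, and covariates could be chosen after the results are known. At stake are the width of the confidence interval, some power, and a clear primary result.

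**Working it through.** **1. The plan's own sample size.** Inputs from Calculation of the sample size: two-sided alpha 0.05, power 0.80, control mean 50%, difference 20%, SD equal to half of each mean. I read the difference as absolute (70 against 50) and the SD as between patients.

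- SDs: 0.5 × 50 = 25 and 0.5 × 70 = 35. Root mean square = sqrt((25² + 35²)/2) = sqrt(925) = 30.41.
- Two-sample t-test (noncentral t): 38 per arm for 80% power. At the planned 40 per arm, power is 82.8%.
- Reading the 20% as relative (60 against 50, SD 27.6) needs 121 per arm and does not fit the plan.

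The planned 80 is reproduced as sufficient without any covariate. No dropout allowance is stated; 38/0.95 = 40, so there is room for about 5% loss.

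**2. Why size could matter for one patient.** Assume a circular lesion of area A with radius R = sqrt(A/π) and edge advance x. Then reduction = 100 × [1 − (1 − x/R)²].

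| Edge advance | 1 cm² | 10 cm² | 99 cm² |
|---|---|---|---|
| 3 mm | 78% | 31% | 10% |
| 5 mm | 99% | 48% | 17% |
| 10 mm | 100% | 81% | 32% |

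This is illustrative geometry, not trial data.

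**3. What adjustment buys.** The residual SD after adjusting for log baseline area is 30.41 × sqrt(1 − r²). The standard error of the arm difference is that SD × sqrt(2/40), where sqrt(2/40) = 0.2236. The part of the unadjusted standard error that comes from chance size imbalance is r × 30.41 × 0.2236. The values of r are assumptions.

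| r | Residual SD | SE of difference | Imbalance part (points) | Power at 40 per arm | n per arm for 80% |
|---|---|---|---|---|---|
| 0 | 30.41 | 6.80 | 0 | 82.8% | 38 |
| 0.2 | 29.80 | 6.66 | 1.4 | 84.2% | 36 |
| 0.3 | 29.01 | 6.49 | 2.0 | 86.1% | 35 |
| 0.4 | 27.87 | 6.23 | 2.7 | 88.7% | 32 |
| 0.5 | 26.34 | 5.89 | 3.4 | 91.8% | 29 |
| 0.6 | 24.33 | 5.44 | 4.1 | 95.3% | 25 |

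The imbalance part lies inside the 6.80 and does not add to it. At r = 0.6, 4.08² + 5.44² = 16.6 + 29.6 = 46.2 = 6.80². At r = 0.1 the adjusted standard error is 30.41 × sqrt(0.99) × 0.2236 = 6.77, practically no change. The standardised size difference between arms has SD 0.22, and exceeds 0.5 SD in about 2.5% of trials.

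**4. How uncertain r is.** Simulations on the circular model, with the mean tuned to 50%, give very different shares of endpoint variance explained by log area (r²), depending on what is assumed:

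- Edge advance with a coefficient of variation of 50%: 29–44% in one set of runs, 40–58% in another with lognormal advance.
- Coefficient of variation of 100–150%: 10–31%.
- 15% of lesions enlarging by 0–100% regardless of size: 2–11%, so the standard error falls by only about 1–6%.

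**5. Validity of the t-test.** A null simulation on a circular model (40 per arm, 20,000 trials, mean correlation with log area −0.27, so r² about 7%) gave a type I error of 5.1% for the unadjusted t-test.

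**The case against.** The strongest reply is that nothing is broken. Allocation is random, the t-test holds its level, the assumed SD of 30.4 is already meant to cover all between-patient variation including lesion size, and 40 per arm gives about 83% power. The regression sentence also follows directly on the area and quality-of-life comparisons, so some adjustment of the primary measure is probably intended. All of this stands, and it limits the point to efficiency and prespecification. It does not supply the missing covariate or say which analysis is primary.

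Three stronger readings are tempting, and the documents do not support them.

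- **Bias or false positives.** A reader might infer that uneven lesion size biases the result. Under random allocation it does not; chance imbalance is ordinary sampling error, already counted in the standard error.
- **Size as the dominant driver of the endpoint.** The geometry makes this plausible for individual patients, but the documents give no size distribution, no closure data and no correlation. Depending on the assumptions, log area explains anything from 2% to 58% of the variance.
- **A need for a minimum lesion area.** Worsening has no floor on the percent scale: a 1 cm² lesion growing to 3 cm² scores −200% and would lower a 40-patient arm mean by (50 + 200)/40 = 6.25 points, compared with a patient at the assumed mean of 50%. But nothing in the documents says how often this happens, and a 2 cm² lesion growing to 6 cm² scores the same, so a small cut-off would not cure it. Where a patient has several eligible lesions, only the largest is recorded, which already moves the analysed lesions away from the smallest sizes. A size limit would change eligibility, and the documents give no basis for one.

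**Conclusion.** The point holds as an avoidable loss of precision and a gap in prespecification, not as a threat to the validity of the trial or to its sample size. Baseline area is collected and is a natural predictor of percent reduction, yet no analysis names it. For an assumed r of 0.2 to 0.6, adjusting for it lowers the standard error of the arm difference from 6.80 to between 6.66 and 5.44 points, and raises power at 40 per arm from 82.8% to between 84.2% and 95.3%. If r is near 0.1 or below, the gain is negligible, and adjustment costs one degree of freedom. These figures rest on the plan's means and SDs, on the absolute reading of the 20% difference, and on an r that the documents do not give.

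**What to change.** In Statistical analysis, state that the primary week-16 analysis is a linear model of percent lesion area reduction on treatment arm, with the logarithm of the V1 photographic lesion area as covariate; that the treatment coefficient, with its confidence interval and two-sided test at 0.05, is the primary result; and that the unadjusted t-test is supportive. Fix this before outcomes are examined by arm.

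The change needs no new measurement, visit or patient, and no change to eligibility or to the planned 80. The only cost is procedural: under the protocol's amendment section, a change classed as substantive suspends the trial until the ethics committees approve it, so the sponsor should settle that classification first.

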The blue light emitted by the device interacts with the endogenous chromophores of the skin, which trigger reactions that lead to the activation of certain cellular pathways. In particular, the wavelength emitted by the device is absorbed by Protoporphyrin IX present in Cytochrome C, an essential protein for cellular respiration at the mitochondrial level. The energy absorbed in this way is used by the cell to increase the production of ATP, a fundamental molecule for all the processes involved in tissue repair. In addition, blue light is able to stimulate the production of ROS (Reactive Oxygen Species) through the excitation of flavins and flavoproteines. Nowadays, multiple evidence has been produced about how ROS can be considered signal transducers of numerous cellular pathways. This consideration validates the evidence that ROS (at physiological concentrations) are crucial for multiple cellular functions such as differentiation, proliferation, migration and contraction.

Literature review and rationale of the clinical investigation

Chronic diseases, such as the development of ulcerative lesions, related to the ageing population, now tend to increasingly burden the NHS and, indirectly, also the families of patients, which are faced with problems such as, in addition to the care of the patient, also the lack of productivity (and profit) due to the need to leave work to accompany the patient to the doctor or to do the therapy.

This and many others are the things to consider, besides the purely medical and biological aspect, when the full impact of a disease on the patient and his family is assessed, before than on the entire population. Wound healing is a complex and dynamic biological process that includes a series of organized phases,

L.U.C.E. Study Protocol version 3.0 (24/02/2020)

including coagulation, inflammation, matrix deposition, angiogenesis, proliferation, cell remodeling and wound contraction (1, 2). So that each step of the

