- Group 2: Experimental treatment group represented by a weekly visit during which the EmoLED treatment is added to the standard treatment in order to assess the clinical efficacy of the two therapies and their impact on economy and quality of life (Qol).

The EmoLED device has received the CE mark (certificate no. G1 18 02 99242 002) and was used, in its prototype version, in three different clinical trials. The first two studies analyzed the effectiveness of EmoLED on surgical lesions (acute), the third study, currently underway, on the basis of some spontaneous observations of professionals in the field, assesses the effectiveness of continuous therapy on chronic injuries.

The clinical safety of the device has therefore been assessed in previous studies which have shown the not inferiority of treatment with EmoLED compared to other advanced therapies.

In the context of this study, venous or mixed skin ulcers will be considered. The application of the treatment in details will be explained later, however the treatment with EmoLED consists in radiating the lesion for 60 seconds with the light emitted by the device.

This treatment does not interfere with other systemic therapies that may be in place, nor does involve any additional risk compared to the standard treatment; the potential benefit is attributable to a reduced time of healing, which is followed by the consequent indirect benefits.

L.U.C.E. Study Protocol version 3.0 (24/02/2020)

Principle of operation of the EmoLED medical device to help wound healing

The EmoLED device is a medical device for the healing of wounds, CE marked, whose operation is based on LED sources operating in the blue range.

The choice of blue light was made on the basis of Anderson and Parrish's theory of selective photothermolysis which states that selective heating of a target chromophore is achieved when the wavelength of the source - our LEDS - is preferentially absorbed by the chromophore - the Protoporphyrin IX of the heme group and of the Cytochrome C.

As for the use of light in medicine, the scientific literature is rich in data and evidence on its use for the treatment of acne (5) and psoriasis (6) and its effectiveness in accelerating the process of healing of an induced wound on animal models (7), (12).

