- Pregnancy or breast feeding;
- Patients with neoplasms or other diseases involving the use of cytostatic or immunosuppressive drugs;
- Patients with limited lifespan;
- Patients with photosensitizing illnesses or that take photosensitizing drugs.

All inclusion and exclusion criteria must be satisfied before recruitment. Any concomitant pharmacological therapy must be maintained.

Number of patients expected to enroll

A total of 80 subjects will be recruited, 40 per arm at the facilities involved in the clinical study. Each one of the four sites involved will enroll 20 patients. The expected time for enrollment is 7 months. Since this is a multicentric investigation with competitive recruitment the number of patients per site can vary, depending on the recruitment capability of each site.

Enrollment point

Once the patient has signed the informed consent, the Principal Investigator enters the data in the Enrollment Registry, carefully checking all the inclusion and exclusion criteria; if all criteria are met, the patient is considered to be enrolled in the clinical study.

Number of experimental devices expected to be used

Each experimental site will be equipped with an EmoLED medical device. In the study a total of 4 EmoLED medical devices will be made available.

Time-frame of the study

The study lasts 12 moths, with a recruitment time of 7 months.

Medical and surgical procedures

The lesions will be cleansed with saline solution and, if necessary, surgical debridement will be performed with the most suitable method. At this point, if patient is included in Group 2, the EmoLED treatment starts. After EmoLED application (Group 2) or after cleansing (Group 1), a polyurethane foam dressing will be applied on the lesion. In case of clinical signs of infection, a silver dressing will be applied.

Then an elasto-compressive double layer dressing of the limb with cohesive fixation bielastic latex-free bandage will be carried out.

The treatment with EmoLED, in addition to the SOC, will be performed during each visit for 60 seconds on each 5 cm diameter sub-area of the selected lesion.

In case of multiple lesions matching with both inclusion and exclusion criteria, they will be all treated following the same protocol, depending on the group to which the patient belongs; in this case the Principal Investigator will fill out a data-collection form and take pictures just of the lesion with the wider area.

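### The protocol gives no ground for withholding EmoLED in a single patient who becomes photosensitized or has a device-related adverse event, and patients who stop attending because of harm are excluded without a week-16 outcome

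*Combined protocol and SAP*

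**What the plan says.** All references are to the combined protocol and SAP.

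- **Delivery.** Medical and surgical procedures: "The treatment with EmoLED, in addition to the SOC, will be performed during each visit for 60 seconds" on each 5 cm sub-area. Measurable parameters, for Group 2: "16 treatments are planned during 16 weeks, 1 per week". No condition for omitting a session is given.
- **Photosensitivity.** Exclusion criteria: "Patients with photosensitizing illnesses or that take photosensitizing drugs". The timing follows the list: "All inclusion and exclusion criteria must be satisfied before recruitment". No re-check during the study is stated.
- **Other drugs.** The next sentence reads "Any concomitant pharmacological therapy must be maintained", most naturally about therapy present at entry. The rationale section adds "This treatment does not interfere with other systemic therapies that may be in place". Drug therapy is an item in the Clinical Section of the Data Collection Form; whether it is asked again at later visits is not stated.
- **Mechanism and risk.** The device description says "the wavelength emitted by the device is absorbed by Protoporphyrin IX" and that blue light stimulates reactive oxygen species. The objectives section says "no risks are reported in addition to the ones related to the use of light in medicine".
- **Withdrawal.** Patients who miss two consecutive weeks up to week 14, or one week after that, are telephoned and excluded from the study if they do not intend to continue. Anyone absent for more than half of the sessions is also excluded. Neither rule mentions harm.
- **Harm.** The adverse event sections record measures taken and whether the event led to withdrawal. They define the highest causality grade by the event receding on stopping the product and returning on restarting it. Events are followed after withdrawal for any reason.
- **Analysis.** The statistics section compares mean area reduction by t-test and names no analysis set.

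**The concern.** The sponsor's own criterion treats photosensitized patients as unsuitable for this light, and that reason does not lapse after enrolment. Over 16 weeks a patient may be prescribed a photosensitizing drug or develop a photosensitizing illness. The protocol then has no instruction except to irradiate at the next visit. The same is true of a patient with a skin reaction attributed to the device.

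Two things are at stake. The first is safety, which is also the first-listed secondary endpoint: sites that stop the device will do so by their own rules, and the highest causality grade depends on stopping and restarting that nobody has planned. The second is the primary comparison. A patient who stops coming because of harm is treated like any other non-attender, and no final photograph is sought.

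**Working it through.** **Step 1. The sections side by side.**

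| Question | Where one would look | What is found |
|---|---|---|
| When is EmoLED given? | Medical and surgical procedures | At each visit, unconditionally |
| When is photosensitivity checked? | Exclusion criteria | Before recruitment |
| When may it be withheld from one patient? | Procedures, withdrawal and adverse event sections | Not stated |
| When is treatment stopped for safety? | Early termination section | At study level only |
| Is a final outcome sought from leavers? | Withdrawal and safety follow-up sections | Adverse events followed; no wound photograph asked for |

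The treatment of infection is a useful contrast. A clearly infected ulcer is an entry exclusion, and the procedures section also says what to do if signs of infection appear on study (a silver dressing). Photosensitivity has the first rule without the second.

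**Step 2. Dose per session.** Power density is 120 mW/cm² (device description) for 60 s: 0.120 × 60 = 7.2 J/cm², matching the protocol's figure of about 7. This is an exposure; it is not evidence of harm.

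**Step 3. Whom the absence rule catches.** With 16 planned Group 2 sessions and *a* attended, the patient is excluded when 16 − *a* > 8, that is, when *a* ≤ 7. A patient who leaves after 8 or more visits does not meet this rule. The telephone rule excludes that patient if the stated number of weeks is missed and the patient will not continue. In Group 1, with 32 sessions, the limit is 15 or fewer attended.

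**Step 4. The plan's power.** Inputs from the sample size section: means 50% and 70% (the 20% difference read as points), SD half of each mean (25 and 35), 40 per group, two-sided α = 0.05.

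- Standard error = √(25²/40 + 35²/40) = 6.80; 20 / 6.80 = 2.94.
- Power from the noncentral t with 78 degrees of freedom = 0.828.
- 38 per group are needed for 0.80, so the stated 40 is sufficient on this reading.

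**Step 5. Possible bias if leavers are also dropped from the analysis.** Suppose *k* of 40 Group 2 patients leave because of device harm with area reduction *y*%, and the others average 70%. Dropping them overstates the Group 2 mean by *k*(70 − *y*)/40.

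| *k* | *y* = 35 | *y* = 0 |
|---|---|---|
| 0 | 0 | 0 |
| 1 | 0.9 | 1.75 |
| 2 | 1.75 | 3.5 |
| 4 | 3.5 | 7.0 |

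For *k* from 1 to 4 that is 0.9 to 7.0 points, or 4% to 35% of the planned 20. Both *k* and *y* are assumptions; the documents give no event rate.

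**Step 6. What withholding would cost in power.** Suppose *m* of 40 patients lose a fraction *f* of the 20-point effect. The difference becomes 20(1 − *mf*/40), with SDs unchanged.

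| *m* | *f* | Difference | Power |
|---|---|---|---|
| 0 | – | 20.0 | 0.828 |
| 1 | 2/16 | 19.94 | 0.825 |
| 4 | 2/16 | 19.75 | 0.818 |
| 1 | 1 | 19.5 | 0.808 |
| 4 | 1 | 18.0 | 0.743 |

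The last row is the extreme: four patients lose the whole effect.

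**The case against.** **The investigator can stop the device.** This is correct. A reader might infer that the protocol compels irradiation of a photosensitized patient, but no sentence forbids withholding. Symptoms are asked about at each visit, isolated deviations are recorded, measures taken are collected, one causality grade presupposes discontinuation, and the trial runs under GCP and the Helsinki Declaration. What remains is that the safe action departs from the written procedure, with no common criterion across sites.

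**The user manual or training may contain a contraindication.** This is quite possible for a CE-marked device with labelling and written instructions. Those materials are not among the documents, so this lowers confidence. A manual would still be unlikely to settle whether the patient stays in the trial and in the analysis.

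**The absence rule does not catch everyone harmed.** Correct. A reader might take every early leaver to be caught by the more-than-half rule; Step 3 shows that later leavers come under the telephone rule. A patient who attends without receiving EmoLED is not absent at all.

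**Exclusion from the study is not exclusion from the analysis.** Also correct. The text says the former, and the forms of withdrawn patients are archived. The missing analysis set affects every dropout, whatever the reason.

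**The direction of bias is not shown.** A reader might infer that the rules favour EmoLED, since device harm can arise only in Group 2. But the absence rules bind both groups, and Group 1 has twice the planned visits. Group 1 patients who leave because of poor healing or visit burden, if dropped, would bias the comparison the other way. The protocol also reports no device-related events in earlier experience, so the number of harmed leavers may be zero.

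**Conclusion.** The concern holds in a limited form, with medium confidence. The safety part rests on the text alone: EmoLED is ordered at every Group 2 visit, photosensitivity is checked only before recruitment, and no patient-level ground for withholding is given. That is worth correcting even if the event is rare, because the sponsor has already judged such patients unsuitable.

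The bias part is conditional. It needs harmed patients to leave, and exclusion from the study to carry into the analysis. Under the assumed 1 to 4 leavers, the Group 2 mean would be overstated by 0.9 to 7.0 points; with none, by nothing. The net effect across both groups cannot be determined from the documents, which therefore do not support a claim that the result will favour EmoLED.

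**What to change.** Add a short paragraph to the procedures and withdrawal sections:

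- (a) At each visit, ask about new drugs and illnesses. Withhold EmoLED while a photosensitizing drug or illness is present.
- (b) Pause EmoLED for a moderate or severe adverse event graded as possibly or undoubtedly correlated, until it resolves. Record the pause and any restart.
- (c) Continue standard care, visits and photographs during any pause. Seek a week-16 photograph from anyone who stops attending. Analyse these patients in their randomized group.

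Add one entry to the Data Collection Form for a session not given, with the reason.

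The cost is a slight dilution of the effect in a few patients. Power falls from 0.828 to 0.825 if one patient loses an eighth of the effect, and to 0.743 only in the extreme case of Step 6. The larger cost is procedural: a substantive amendment suspends the trial until the ethics committees approve it, so this change should be bundled with any others.
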